Patient population	
80 patients with prostate cancer who have recently started (within 6 months of study entry) or plan to pursue androgen deprivation therapy (ADT), with an expected duration of therapy of at least 12 months following study enrollment, will be eligible to participate in the randomized study. Twenty (20) patients currently receiving or planning to start combined chemohormonal therapy will be eligible to participate in the non-randomized pilot cohort.
 
Key Eligibility Criteria:
 
 • Histologic confirmation of adenocarcinoma of the prostate • Receiving or planning to receive ADT with LHRH agonist or antagonist • Expected duration of ADT at least 12 months from study entry • Concurrent antiandrogen therapy allowed but not required • First dose of LHRH agonist or antagonist no more than 6 months prior to study entry • Prior/concurrent radiation therapy allowed • Physically able to participate in exercise program • Willing and able to travel to UCSF for monthly visits • Randomized cohort only: 
 ○ No prior chemotherapy within 12 months of start date of study 
 ▪ No planned chemotherapy during the initial 12 month period of study participation • Non-randomized pilot cohort: 
 ○ Concurrent chemotherapy (initiated within 3 months of study entry) or planned chemotherapy within 3 months of study entry
Rationale for Study	
Androgen deprivation therapy (ADT) is the most common systemic therapy applied in prostate cancer. It is associated with improvement in overall survival, regression of tumors, and symptom palliation in various disease states including concurrently with radiation therapy, following surgery, and for patients with metastatic disease. However, ADT is associated with numerous changes in body composition and metabolic perturbations leading to significant iatrogenic morbidity and mortality. ADT is associated with the development of the metabolic syndrome, increases in body fat, decrease in lean body mass, weight gain, hyperlipidemia, insulin resistance/diabetes, and, potentially, an increased risk of cardiovascular morbidity and mortality. It also impacts quality of life via muscle wasting, hot flashes, gynecomastia, sexual dysfunction, mood, and relationship changes. Given the broad spectrum of ADT-associated toxicities across numerous domains, there is a clear unmet medical need to develop systematic, multi-disciplinary approach to partially mitigate the toxicity of ADT.
 
Many of ADT-associated toxicities are modifiable with careful management, although current practice data suggest that the vast majority of physicians who prescribe ADT do not manage these side effects in a consistent way, if at all. Multiple prior studies in the primary care setting demonstrate that integrated, multi-disciplinary efforts as compared to routine counseling during physician visits lead to more substantial changes in lifestyle habits, including improved diet, smoking cessation, and blood pressure management. Therefore, comprehensive management of the potential side effects of ADT with the use of a multi-disciplinary clinic may improve outcomes and partially reverse the side effects of ADT, as compared to usual standard of care.
 
The “STAND (Supportive Therapy in ANdrogen Deprivation)” Clinic at UCSF was created for patients treated with ADT to address and mitigate the adverse effects of hormone therapy. The intent is to provide “one stop shopping” and provide patient navigation across a number of

	
different disciplines, clinics and services.
 
During the course of an integrated visit, the patient will have the following personalized assessment and counseling:
 
 • Patient care and counseling by a trained nurse practitioner and/or physician • Twelve monthly educational “modules” regarding ADT side effect management • Medication management including LHRH analogue injections during visit • Cardiovascular monitoring and risk reduction, including hypertension, hyperlipidemia, glucose monitoring, and cardiac risk stratification • Bone health monitoring and management • Nutrition counseling • Exercise training • Evaluation and counseling for relationship and mood changes by trained social worker • Assessment of quality of life and side effects of ADT with validated questionnaires (patients will also have opportunity to fill out questionnaires on-line ahead of clinic visit) 
The current randomized phase 2 cross-over study is designed to preliminary evaluate the longitudinal impact of participation in the “STAND” clinic (as compared to usual standard of care) on key metabolic parameters, quality of life, and patient satisfaction for men receiving hormone therapy for prostate cancer. Standard-of-care therapy will consist of every 3-month visits comprised of review of medical history, toxicity assessment, and lifestyle modification counseling provided by individual health care provider, LHRH analog injections by trained oncology nurse. Patients will have access to exercise, nutrition, and social work counseling if requested by patient or deemed necessary after consultation with health care provider. After 12 months on study, patients randomized to the usual standard-of-care arm will have the opportunity to cross-over and participate in the STAND clinic for the ensuing 12 months or for the remainder of ADT duration, whichever is shorter. Should the results indicate a beneficial impact of participation in a multi-disciplinary clinic in mitigating the short- and intermediate-term toxicities of ADT, this would form the justification for larger randomized clinical trials to assess the impact of clinic participation on longer-term co-morbidities including the incidence of diabetes, cardiovascular morbidity and mortality, and overall incidence of non-prostate cancer specific mortality.


Primary Objective
	
Randomized cohort: To compare the mean percent change from baseline to 12 months in percentage body fat mass among men with prostate cancer receiving androgen deprivation therapy randomized to participate in the “STAND” clinic vs. usual standard of care.
 
Non-randomized pilot cohort: To determine the feasibility of completing multi-disciplinary STAND clinic visits while undergoing concurrent chemohormonal therapy for prostate cancer.

Secondary Objectives
	
To compare the mean percent change from baseline to 12 months and patterns of change over time during participation in the STAND clinic vs. usual standard of care with respect to:
 
Metabolic Impact on Diabetes and Cardiovascular Risk Factors:
 
 - Fasting blood glucose - Fasting plasma insulin level - Insulin resistance as calculated by HOMA-IR - Hemoglobin A1c - Fasting lipids (total cholesterol, LDL, HDL, triglycerides) - Waist circumference - Body weight/body mass index - Exercise patterns as measured by validated questionnaire and home-based accelerometer assessment - Blood pressure

	
Bone Health:
 
 - Bone density as assessed by DXA scan - 25-(OH) vitamin D serum levels 
Quality of Life/Psychosocial Impact:
 
 - Depression as measured by PHQ-9 - Cognitive function as measured by the Attentional Functional Index - Overall quality of life as measured by SF-12 - Fatigue as measured by Lee Fatigue Scale - Erectile and urinary function as measured by EPIC-26 - Hot flash severity as measured by Hot Flash Related Daily Interference Scale 
Among men randomized to receive usual standard of care that cross-over to participate in the STAND clinic after month 12 of the study:
 
To measure the mean change from baseline at start of participation in the STAND clinic after 12 months of participation in:
 
 - Metabolic parameters including percentage body fat, fasting insulin/glucose, HOMA-IR, body weight/body mass index, waist circumference - Bone health - Quality of life 
Among men in the non-randomized pilot cohort:
 
 - To determine the mean change from baseline to 12 months during STAND clinic participation in the primary and secondary metabolic and quality of life parameters listed above.
Correlative Study Objectives	
 • To investigate for a relationship between inherited genetic polymorphisms of functional relevance near or within genes encoding proteins with roles in steroid hormone transport and androgen receptor signaling with changes in metabolic parameters among men treated with androgen deprivation therapy. • To investigate changes in trabecular bone micro-architecture as measured by High Resolution Peripheral QCT Imaging of radius and tibia during androgen deprivation therapy. • To investigate for relationship between 2nd digit to 4th digit length ration (2D:4D ratio) and percent change from baseline in quality of life metrics on androgen deprivation therapy. • To investigate for a relationship between 2nd digit to 4th digit length ratio and baseline empathy score as measured by validated questionnaire.
Study Design	
Randomized, phase 2 study with cross-over design to assess the longitudinal impact of the multi-disciplinary STAND clinic on changes in key metabolic parameters, quality of life, and patient satisfaction among men receiving androgen deprivation therapy for prostate cancer. A non-randomized pilot cohort of patients receiving concurrent chemohormonal therapy will be enrolled in parallel to assess the feasibility of STAND clinic participation in this patient population.
 
Randomized study schema:

	
N = 80 patients (40 patients per study arm)
 
 - Planned or ongoing treatment with LHRH agonist/antagonist with or without concurrent anti-androgen - ADT initiated within 6 months of day 1 of study entry - Expected duration of ADT at least 12 months from date of study entry 
Stratification Factors:
 
 1) Duration of ADT Prior to Study Entry (0-3 vs. 3-6 months) 2) Body mass index (< 30 vs. ≥ 30) 
Primary Endpoint: Mean Percent Change From Baseline in Percentage Body Fat
 
12 Months
 
Randomize 1:1
 
"STAND" Multidisciplinary Clinic
 
Usual Standard of Care
 
12 Months or Duration of ADT
 
Optional Cross-Over to Participate in "STAND" Clinic
 
12 month Cut-Point for Primary Study Analysis


Number of patients
	
80 patients with prostate cancer who are expected to receive at least 12 months of androgen deprivation therapy from the date of study enrollment will be enrolled.
 
A separate non-randomized patient cohort of 20 patients who are receiving concurrent chemohormonal therapy will be enrolled in parallel.

Duration of study
	
Patients randomized to participate in the STAND clinic will be followed for 12 months. Men initially randomized to the usual standard-of-care will have the option to cross-over onto participation in the STAND clinic after month 12, and will be followed in the STAND clinic for an additional 12 months or until 6 months following last dose of ADT, whichever is shorter. Patients enrolled in the non-randomized chemohormonal cohort will participate in STAND clinic for 12 months.

Study Assessments
	
In the STAND clinic treatment arm, patients will have every 3 month visits with a health care provider, along with monthly educational modules, and multi-disciplinary assessment and counseling by exercise, nutrition, and symptom management service on a rotating schedule. In the usual care treatment arm, patients will have every 3 month visits with their usual health care provider, and will have unrestricted access to exercise, nutrition, and symptom management services upon patient request or as deemed necessary by health care provider. In the non-randomized chemohormonal cohort, patients will have schedule modified as necessary to fit with chemotherapy dosing schedule but will have on average every 3 month counseling with physical therapist, nutrition, and symptom management.


Study Endpoints
	
Primary Endpoint
 
Randomized cohort: Mean percent change from baseline to 12 months in percentage body fat mass as measured by bioelectrical impedance analyzer.
 
Non-randomized cohort: Percentage of completed STAND clinic visits during the course of the 12 month STAND clinic participation.
 
Secondary Endpoints Mean percent change from baseline to 12 months and patterns of change from baseline with respect to the following:
 
Metabolic Impact on Diabetes and Cardiovascular Disease Risk Factors:
 
 - Fasting blood glucose - Fasting plasma insulin level - Insulin resistance as calculated by HOMA-IR - Hemoglobin A1c - Fasting lipids (total cholesterol, LDL, HDL, triglycerides) - Waist circumference - Body weight/body mass index - Exercise patterns as measured by validated questionnaire and ambulatory accelerometer assessment - Blood pressure 
Bone Health:
 
 - Bone density at the lumbar spine, femoral neck, and total hip as assessed by DXA scan among patients without bone metastases at the time of study entry - Serum 25-(OH) vitamin D levels 
Quality of Life/Psychosocial Impact:
 
 - Depression as measured by PHQ-9 - Cognitive function as measured by Attentional Functional Index - Overall quality of life as measured by SF-12 - Fatigue as measured by Lee Fatigue Scale - Erectile and urinary function as measured by EPIC-26 - Hot flash severity as measured by Hot Flash Related Daily Interference Scale 
Correlative Study Endpoints:
 
 • Association between inherited genetic polymorphisms of functional relevance near or within genes encoding proteins with roles in steroid hormone transport and androgen receptor signaling with changes in metabolic parameters among men treated with androgen deprivation therapy. • Mean change from baseline in trabecular bone architecture as measured by trabecular bone number (TbN) and trabecular bone volume fraction (BV/TV) after 12 months of androgen deprivation therapy.
-------------------------------	---

List of Abbreviations

AE	Adverse event
CHR	Committee on Human Research (UCSF IRB)
CRC	Clinical Research Coordinator
CTMS	Clinical Trial Management System
DSMC	Data and Safety Monitoring Committee
DSMP	Data and Safety Monitoring Plan
FDA	Food and Drug Administration
GCP	Good Clinical Practice

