8.3 Germline Polymorphisms

Collection of peripheral blood mononuclear cells for assessment of germline polymorphisms and their association with the relevant toxicities of ADT is an exploratory objective of the current study and patient participation in this aspect of the study is optional.

The genetic polymorphisms selected for this study were based on a literature review of prior studies which demonstrated significant associations between polymorphisms near or within select genes of interest encoding proteins involved in steroid hormone metabolism, intra-cellular transport, estrogen/androgen receptor signaling, and the IGF pathway with clinical outcomes on androgen deprivation therapy. Most prior studies included polymorphisms with a minor allele frequency > 5% in the CEU (Caucasian) population. The full set of polymorphisms to be analyzed is listed in Appendix 1.

Genomic DNA will be prepared from peripheral blood using a QIAamp DNA Blood Mini Kit (Quiagen Inc, Valencia, CA, USA). DNA will be stored at 4°C. Genotyping will be carried out using Sequenom iPLEX matrix-assisted laser desorption/ionization (MALDI)-time of flight mass spectrometry technology (Carlsbad, CA; http://www.sequenom.com/seq_genotyping.html/). Assays will be designed using Sequenom's MassARRAY AssignDesigner application, version 3.0. Polymerase chain reaction (PCR) and single base extension (SBE) oligonucleotides will be synthesized by Integrated DNA Technologies (Coralville, IA). PCR amplification will be performed using an input of 10 ng of DNA in a final volume of 6 L. The PCR products will be subsequently treated with shrimp alkaline phosphatase, and the SBE reactions will be initiated using iPLEX enzyme and mass-modified terminators (both Sequenom). After desalting, 7 nL of the SBE reaction will be spotted onto a SpectroCHIP (Sequenom) preloaded with 7 nL of 3-

hydroxypicolinic acid matrix. The SpectroCHIPs will be analyzed in automated mode by a MassArray Compact solid phase laser mass spectrometer system (Bruker Daltonics, Billerica, MA). The resulting spectra will be analyzed and genotypes called in real-time by the SpectroCaller algorithm, followed by additional user-initiated analysis with the SpectroTyper v.3.4A (Sequenom). The error rate on this platform is estimated to be less than 0.03%.

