9.6 Demographics and Baseline Characteristics

Demographic variables will include age, race, and ethnicity. Baseline characteristics will include the following:

- Height, weight, body mass index, waist circumference, percentage body fat
- Assessment of co-morbidities including diabetes and heart disease (Appendix 3)
- Date of prostate cancer diagnosis
- Gleason grade and PSA at the time of diagnosis
- Type and date of prior local therapy (if any)
- Date of ADT initiation and indication (adjuvant, biochemical relapse, or metastatic disease)
- Baseline PSA at the start of ADT
- Concurrent use of anti-androgen
- Metastatic status at time of study entry (none, bone only, soft tissue, any visceral)

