9.8.3 Analytic Plan for the Correlative Objectives

The relationship between each pre-selected SNP genotype and the percent change from baseline to 12 months on-study in percentage body fat, fasting plasma glucose, body mass index, waist circumference, and fasting insulin among men undergoing ADT will each be tested using a two-sample t test or Wilcoxon-rank-sum test as appropriate when the SNPs are in dominant or recessive fashion. When SNPs are in the additive model, for each SNP, a generalized linear model with an appropriate link will be used considering each baseline-12 month change as the response variable and SNP genotype (coded as 0, 1, and 2 for zero, one and two copies of minor allele) as the predictor. Analysis will be extended to adjust for possible risk factors by fitting multivariate generalized linear models for each baseline-12 month change and each SNP. Multiple testing adjustments will be done for each baseline-12 month change across all SNPs by controlling for false discovery rate.

The mean percent change from baseline in trabecular bone microarchitecture parameters including trabecular bone number and trabecular bone volume assessed by high resolution quantitative peripheral CT will be descriptively reported for the entire study population. In an exploratory fashion, the mean percent change between those randomized to the STAND versus usual care treatment arms will be compared using Mann-Whitney test.

The distribution of the 2D:4D finger length ratio will be determined for the entire study population. As the optimal cut-off to define sensitivity to androgen deprivation therapy is not known, the study cohort will be dichotomized into those with 2D:4D ratios above and below the median respectively. The mean percent change from baseline in QOL scores from the collected questionnaires as well as the baseline and mean percent change from baseline in empathy score will be compared between dichotomized subgroups using the Mann-Whitney test.

No adjustment for multiple comparisons will be made for the analysis of the correlative study endpoints.

10. Study Management

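### Section 9.8.3 tests each SNP without adjusting for ancestry, and its planned covariate extension names no covariates, so an exploratory SNP finding could reflect ancestry group instead of genotype

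*Combined protocol and SAP*

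**What the plan says.** The endpoint, "Association between inherited genetic polymorphisms of functional relevance near or within genes encoding proteins with roles in steroid hormone transport" and androgen receptor signaling with metabolic change, is defined in the Abstract (Correlative Study Endpoints) and again in 3.2.3 and 9.7.3. The tests are in 9.8.3, which relates each SNP to the 12-month change in five measures: percentage body fat, fasting glucose, body mass index, waist circumference and fasting insulin.

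- Dominant or recessive coding: the relationships "will each be tested using a two-sample t test or Wilcoxon-rank-sum test as appropriate when the SNPs are in dominant or recessive fashion".
- Additive coding: a generalized linear model with "SNP genotype (coded as 0, 1, and 2 for zero, one and two copies of minor allele) as the predictor".
- Adjustment: "Analysis will be extended to adjust for possible risk factors by fitting multivariate generalized linear models for each baseline-12 month change and each SNP". No risk factor is listed.
- Multiplicity: a false discovery rate step across SNPs for each outcome. The last sentence of 9.8.3 then says that correlative endpoints get no multiplicity adjustment.

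On ancestry, 9.6 states "Demographic variables will include age, race, and ethnicity", but no model in 9.8 uses race or ethnicity. Sections 4.1 and 4.2 set no restriction on either. Section 8.3 describes the marker choice as follows: "The genetic polymorphisms selected for this study were based on a literature review of prior studies". It adds: "Most prior studies included polymorphisms with a minor allele frequency > 5% in the CEU (Caucasian) population". Appendix 1 lists 12 candidate polymorphisms. No ancestry-informative markers or principal components are planned.

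Section 1.3.5.1 says that the sample size allows only an exploratory SNP analysis, and 8.3 makes genotyping optional for patients.

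**The concern.** A genotype comparison pooled over men of different ancestry is open to ordinary confounding. Suppose that one group carries the minor allele more often and also changes more, or less, over 12 months. Carriers and non-carriers then differ in mean change even if the SNP does nothing.

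The false discovery rate step does not repair this. It takes the p-values as valid under the null, and confounding makes them too small. One outcome difference between groups can bias every marker whose frequency differs between those groups.

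An analyst could follow 9.8.3 to the letter and never adjust for ancestry, or could choose the covariates after seeing results. At stake is which variants are carried forward as candidate predictors of ADT toxicity. Section 1.3.5.1 has in mind eventual use in clinical decisions, so a lead that only marks ancestry would be a poor one to pass on.

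**Working it through.** **The plan's own figures.** The documents state no sample size, power or error rate for the SNP analysis, so there is no figure to reproduce. From 9.2 come the numbers of men, 64 evaluable (2 × 32) and 80 enrolled (2 × 40), and the primary-endpoint SD of 17% with a mean change of 12%. From 9.8 comes the 0.05 level.

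**Assumed inputs.** Two ancestry groups, with the second a share *p* of the men. Minor allele frequency is *q1* in the first group and *q2* in the second. The difference in mean 12-month change is *d*, in units of the within-group SD. The SNP has no effect. None of these values is in the documents.

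**Formula, additive coding.**
- Cov(G,Y) = p(1−p) × 2(q2−q1) × d
- Var(G) = 2[(1−p)q1(1−q1) + p·q2(1−q2)] + 4p(1−p)(q2−q1)²
- Var(Y) = 1 + p(1−p)d²
- r = Cov / √(Var(G)·Var(Y)), shift of the test statistic = r√N
- Per-test error ≈ P(Z > 1.96 − shift) + P(Z < −1.96 − shift)

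**Upper case: p = 0.3, q 0.1 versus 0.5, d = 0.5, N = 80.**
- Cov = 0.21 × 0.8 × 0.5 = 0.084
- Var(G) = 2(0.063 + 0.075) + 0.1344 = 0.4104
- Var(Y) = 1 + 0.21 × 0.25 = 1.0525
- r = 0.084 / √(0.4104 × 1.0525) = 0.128; shift = 0.128 × √80 = 1.14
- Error ≈ 0.208

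The same steps for other settings are shown beside a simulation of 4,000 replicates per setting (Monte Carlo SE about 0.003 at 5%, about 0.006 at 20%):

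| N | p | q1 / q2 | d | Formula | Simulated, unadjusted | Simulated, group term added |
|---|---|---|---|---|---|---|
| 80 | 0.1 | 0.1 / 0.3 | 0.3 | 0.055 | 0.049 | 0.046 |
| 80 | 0.2 | 0.1 / 0.3 | 0.5 | 0.086 | 0.093 | 0.056 |
| 64 | 0.3 | 0.1 / 0.5 | 0.5 | 0.176 | 0.188 | 0.046 |
| 80 | 0.3 | 0.1 / 0.5 | 0.5 | 0.208 | 0.202 | 0.045 |

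Dominant coding behaves alike: 0.053, 0.091, 0.165 and 0.185 in the same four rows.

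**Both differences are needed.** If q1 = q2 or d = 0, Cov = 0 and the formula gives 0.05. The simulated error in those settings was 0.044 to 0.057.

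**Fewer genotyped men.** With the upper-case inputs and an assumed N = 40, the shift is 0.128 × √40 = 0.81 and the error about 0.128.

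**What adjustment can do.** The last column gives the model the true group label, so it shows the best case. A harder case has three groups (70/15/15%, allele frequency 0.10/0.50/0.10, outcome shifts 0/+0.5/−0.25 SD, all assumed). With the two smaller groups collapsed into one category, the error falls only from about 12% to between 9% and 10% at N = 64, and from about 14% to 11% at N = 80. With the three groups kept apart it is about 5%.

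**The case against.** The best defence is that 9.8.3 does commit to adjusted models for every SNP and every outcome, and race and ethnicity are on file to enter them. A reader might infer that the plan ignores ancestry altogether. The text does not support that: the extension neither includes nor excludes race. What it lacks is a named covariate and a statement of which model counts. Section 9.8.1, by contrast, names its covariates for the body-fat model (Charlson score, age, baseline PHQ-9, stratification factors).

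A reader might also infer from 8.3 that the markers were chosen in a Caucasian population and that this causes the bias. Neither follows. Section 8.3 describes a literature review and attributes the CEU frequency filter to most of the source studies. Confounding depends on allele frequencies and outcome changes among the enrolled men, however the markers were found.

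The size is also open to challenge, and this part stands. The outcomes are within-person changes, so a stable difference in level between groups does no harm; the groups must differ in change. For body fat, 0.5 SD is 0.5 × 17 = 8.5 points, or 8.5/12 = 71% of the whole mean change that 9.2 expects. Nothing in the documents points to a difference that large. A still larger assumed difference of 0.71 SD, about equal to the trial's full design effect, gave 0.345 in the upper setting (additive coding, N = 80). That is too demanding to serve as a guide.

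Finally, the analysis is exploratory and optional, and no primary or secondary conclusion rests on it.

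**Conclusion.** The point holds as a low-severity weakness of method. The main SNP tests are unadjusted, the extension leaves its covariates open, and no rule says which result supports a declared association. Per-test error for a null SNP is about 5% under mild group differences, about 9% in a middle case, and about 20% in the upper case with 80 men. It is lower if fewer men consent to genotyping. All of these figures rest on assumed ancestry shares, allele frequencies and outcome differences, so they show what could happen and do not estimate what will.

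It would go too far to say that adding race restores the nominal level. That is true only when the model has the right groups. Self-reported race reduces the confounding, and collapsing unlike groups can leave a good part of it.

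**What to change.** In 9.8.3:

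1. Make the main model for each SNP a linear model for the 12-month change (rank-transformed where needed) with the genotype coding plus self-reported race/ethnicity, in place of the unadjusted t or Wilcoxon test.
2. State that this model supports any declared association. If the extension to further risk factors is kept, list the covariates in advance.
3. Apply the false discovery rate step to this model's p-values. For this to be clear, the closing sentence of 9.8.3 on no multiplicity adjustment must be reconciled with the false discovery rate sentence.
4. Collapse race/ethnicity categories only where they are too sparse to fit.
5. Add a sensitivity analysis within the largest single race/ethnicity group, and report the remaining confounding as a limitation.

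The cost is a few sentences and a few degrees of freedom. No new data are needed, because 9.6 already provides for race and ethnicity. The single-group analysis will be small and is there to check direction and size, not significance.
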